9.2.1.1. Adverse Events of Special Interest

The following adverse events of special interest will be evaluated in particular to determine the safety and tolerability of ixekizumab over the range of doses selected for this clinical study.

Adverse events of special interest for ixekizumab are:

- cytopenias (leukopenia, neutropenia, and thrombocytopenia)
- liver function test changes/enzyme elevations (ALT, AST, bilirubin, and ALP)
- infections
- injection-site reactions
- allergic reactions/hypersensitivities
- cerebrocardiovascular events
- malignancies
- depression and suicide/self-injury
- inflammatory bowel disease (Crohn's disease and UC)
- interstitial lung disease (ILD)

Sites will provide details on some of these AEs as instructed on the eCRF. Investigators will also educate patients and/or caregivers about the symptoms of allergic/hypersensitivity reactions and will provide instructions on dealing with these reactions (see Section 7.8.3).

Data on cerebrocardiovascular events will be collected and the events will be adjudicated by an external Clinical Events Committee (CEC) made up of a chairman, 2 cardiologists, and a neurologist.

- Cerebrocardiovascular events are defined as:
 - Death (Cardiovascular)
 - \circ MI
 - Hospitalization for Unstable Angina
 - Hospitalization for Heart Failure
 - o Serious Arrhythmia
 - Hospitalization for Hypertension
 - Resuscitated Sudden Death
 - o Cardiogenic Shock due to MI
 - o Coronary Revascularization Procedure
 - Neurologic
 - Cerebrovascular Event: Transient Ischemic Attack or Stroke (Hemorrhagic, Ischemic and Undetermined)
 - Peripheral Vascular Events
 - o Peripheral Arterial Event
 - o Peripheral Revascularization Procedure

Data on suspected IBD, as identified by events possibly indicative of UC and Crohn's disease, will be collected and the events will be adjudicated by an external CEC made up of gastroenterologists with expertise in IBD.

The role of the CEC is to adjudicate defined clinical events, in a blinded, consistent, and unbiased manner throughout the course of a study. The importance of the CEC is to ensure that all events that have been reported are evaluated uniformly by a single group.

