Infections	
Infections are events including all infections (defined using all the MedDRA PTs from the Infections and infestations SOC), serious infections, potential opportunistic infections, and infections resulting in anti-infective medication administration (i.e., antibacterial, antiviral, antifungal, antiparasitic treatment.). The relationship between TEAE infections and other clinical, laboratory, and hematology parameters will be examined using Spotfire tool.
	
Open-Label Treatment Period (Safety Population): TEAE by PT TEAE by maximum severity by PT* SAE by PT*

Special Safety Topic	Definition/Derivation	Analysis/Summary/Listing
		
AEs leading to discontinuation of study drug*
 
*Included in overall TEAE by maximum severity, SAE and DCAE.

	
Anti-infective medications are defined in Appendix 8 including antibiotics, antifungals, antivirals, or antiprotozoals.
	
	
The OIs are defined in Appendix 9. This list contain PTs as contained within Categories (narrow or broad) from the Infections and Infestations SOC and from the Investigations SOC that can assist in identifying potential OIs. The narrow terms are considered OIs unless medical review determines that the reported term is not consistent with the patient’s clinical history/presentation/course. Medical review of broad terms is needed for final determination of patients meeting the program definition of OIs.
 
The number and percentage of patients with TEAEs that represent potential OIs and as potential OIs will be summarized by treatment group using MedDRA PT nested within categories. Events will be ordered by decreasing frequency in the ixekizumab group nested within categories.
	
Open-Label Treatment Period (Safety Population): TEAE of OIs by PT within category
 
Listing: TEAE of OIs

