
Special Safety Topic	Definition/Derivation	Analysis/Summary/Listing
	
 • ACD: events based on meeting Category A, Category C, and Category D (but no other category) • BCD: events based on meeting Category B, Category C, and Category D (but no other category) • ABCD: events based on meeting each of the 4 Criterion 2 categories 
Summaries of treatment-emergent anaphylactic AEs will be provided for patients meeting each of the 2 criteria and for patients who meet either criteria overall. Separate summaries will be provided for TEAEs by maximum severity, SAEs, and AEs resulting in study drug discontinuation. Severity of treatment-emergent Criterion 2 anaphylactic AEs will be based on the maximum severity of the specific events met by the patient. Maximum severity of an (overall) treatment-emergent anaphylactic AE will be based on the maximum severity within Criterion 1 and/or Criterion 2.
 
Allergic Reactions/Hypersensitivity Events, Non-Anaphylaxis: TEAEs of allergic reaction/hypersensitivity categorized as non-anaphylaxis events are defined by the narrow terms within Hypersensitivity SMQ (20000214) excluding the PTs noted in Appendix 11 and excluding the anaphylactic events as defined above.
	

Special Safety Topic	Definition/Derivation	Analysis/Summary/Listing
Injection Site Reactions	
Injection site reaction is defined using the PTs from the MedDRA HLT of Injection site reactions as defined by MedDRA excluding the following 10 PTs:
 
 1) Embolia cutis medicamentosa 2) Injection site joint discomfort 3) Injection site joint effusion 4) Injection site joint redness 5) Injection site joint infection 6) Injection site joint inflammation 7) Injection site joint movement impairment 8) Injection site joint pain 9) Injection site joint swelling 10) Injection site joint warmth. 	
Open-Label Treatment Period (Safety Population): TEAE by PT within HLT TEAE by maximum severity by PT within HLT AE leading to discontinuation of study drug within HLT

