Appendix 10. Allergic Reactions/Hypersensitivity MedDRA Preferred Term List

Allergic reactions/hypersensitivities will be defined using the following MedDRA Preferred Terms as defined in MedDRA:

- Broad and narrow terms in the Anaphylactic reaction SMQ (20000021)
- Broad and narrow terms in the Angioedema SMQ (20000024)
- Broad and narrow terms in the Severe cutaneous adverse reactions SMQ (20000020)
- Broad and narrow terms in the Hypersensitivity SMQ (20000214), excluding the preferred terms as noted below.

Preferred Terms (MedDRA v.21.0) from Hypersensitivity SMQ Excluded from Analysis	
Administration site dermatitis	Injection site rash
Administration site eczema	Injection site recall reaction
Administration site rash	Injection site urticaria
Administration site recall reaction	Injection site vasculitis
Allergic otitis externa	Instillation site hypersensitivity
Allergic otitis media	Instillation site rash
Allergic sinusitis	Instillation site urticaria
Allergic transfusion reaction	Iodine allergy
Allergy alert test positive	Mast cell degranulation present
Allergy test positive	Medical device site dermatitis
Allergy to surgical sutures	Medical device site eczema
Allergy to vaccine	Medical device site hypersensitivity
Anaphylactic transfusion reaction	Medical device site rash
Antiallergic therapy	Medical device site recall reaction
Application site dermatitis	Medical device site urticaria
Application site eczema	Nodular rash
Application site hypersensitivity	Pathergy reaction
Application site rash	Radioallergosorbent test positive
Application site recall reaction	Reaction to azo-dyes
Application site urticaria	Reaction to colouring
Application site vasculitis	Shock
Arthritis allergic	Shock symptom
Aspirin-exacerbated respiratory disease	Skin test positive
Asthma-chronic obstructive pulmonary disease overlap syndrome	Solvent sensitivity
Blepharitis allergic	Stoma site hypersensitivity
Blood immunoglobulin E abnormal	Stoma site rash
Blood immunoglobulin E increased	Urticaria contact
Bromoderma	Urticarial vasculitis
Catheter site dermatitis	Vaccination site dermatitis
Catheter site eczema	Vaccination site exfoliation
Catheter site hypersensitivity	Vaccination site eczema
Catheter site rash	Vaccination site hypersensitivity
	Vaccination site rash

Preferred Terms (MedDRA v.21.0) from Hypersensitivity SMQ Excluded from Analysis	
Catheter site urticaria	Vaccination site recall reaction
Catheter site vasculitis	Vaccination site urticaria

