Appendix 11. Lilly-Defined MedDRA V21.0 Preferred Terms for Inflammatory Bowel Disease (IBD)

Condition	Preferred Term (MedDRA version 21.0)	Lilly-Defined Classification
Inflammatory bowel disease	Inflammatory bowel disease	Narrow
Crohn's disease	Crohn's disease	Narrow
Ulcerative colitis	Acute haemorrhagic ulcerative colitis	Narrow
	Colitis ulcerative	Narrow
	Proctitis ulcerative	Narrow
Non-specific terms	Abscess intestinal	Broad
	Anal abscess	Broad
	Anal fistula	Broad
	Anal fistula excision	Broad
	Anal fistula infection	Broad
	Anovulvar fistula	Broad
	Aorto-duodenal fistula	Broad
	Colitis	Broad
	Colon fistula repair	Broad
	Colonic fistula	Broad
	Diverticular fistula	Broad
	Duodenal fistula	Broad
	Enterocolitis haemorrhagic	Broad
	Enterocolonic fistula	Broad
	Enterocutaneous fistula	Broad
	Enterovesical fistula	Broad
	Gastrointestinal fistula	Broad
	Gastrointestinal fistula repair	Broad
	Fistula of small intestine	Broad
	Intestinal fistula	Broad
	Intestinal fistula infection	Broad
	Intestinal fistula repair	Broad
	Jejunal fistula	Broad
	Large intestinal ulcer perforation	Broad
	Rectal fistula repair	Broad
	Faecal calprotectin abnormal	Broad
	Faecal calprotectin increased	Broad
	Proctitis haemorrhagic	Broad
	Pseudopolyposis	Broad
	Rectoprostatic fistula	Broad
	Rectourethral fistula	Broad

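### SAP Table RHCF.6.7 sends four safety definitions to the wrong appendix, and the SAP gives two scopes for hypersensitivity without saying which governs

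*SAP*

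**What the plan says.** Protocol section 9.2.1.1 lists "allergic reactions/hypersensitivities" among the adverse events of special interest.

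SAP section 6.15.3.1, Table RHCF.6.7, splits the topic into anaphylaxis and non-anaphylaxis and limits it to events not localized to the injection site. Anaphylaxis is identified by Criterion 1 (six named terms from the Anaphylactic reaction SMQ) or Criterion 2 (events from at least two of four symptom categories). Non-anaphylaxis events "are defined by the narrow terms within Hypersensitivity SMQ (20000214) excluding the PTs noted in Appendix 11", with the anaphylactic events also removed.

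SAP Appendix 10 opens differently: "Allergic reactions/hypersensitivities will be defined using the following MedDRA Preferred Terms as defined in MedDRA". It then names four SMQs: Anaphylactic reaction, Angioedema, Severe cutaneous adverse reactions, and Hypersensitivity. Each is taken with broad and narrow terms. The last entry reads "Broad and narrow terms in the Hypersensitivity SMQ (20000214), excluding the preferred terms as noted below", and the list that follows is headed "Preferred Terms (MedDRA v.21.0) from Hypersensitivity SMQ Excluded from Analysis".

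Appendix 11 is the IBD term list. Elsewhere in Table RHCF.6.7 the pointers continue in the same pattern, for example "The OIs are defined in Appendix 9", although the opportunistic-infection list is Appendix 8.

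**The concern.** A programmer works from the rule in the table. Here the rule names an exclusion list that has nothing to do with hypersensitivity, and the appendix that holds the right list opens with a wider definition of the same topic. Two careful teams could therefore produce two different event sets for one special-interest topic.

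Fisher's exact test is applied to all adverse events (SAP 6.15). Hypersensitivity is also tested within seven subgroup factors, with treatment interactions judged at 0.10 (SAP 6.16.1). Injection-site reactions are a separate special-interest topic, so the same event could be counted under both. Any misclassification need not cancel between arms, because a full course is 14 or 17 injections on ixekizumab and 26 or 28 on adalimumab (SAP 6.10). The trial is open-label, so it is better that the definition leaves no choice to be made once data are in view.

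**Working it through.** No sample size, power or event count bears on this, so the check is a trace of the references and a comparison of the lists.

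**1. Pointers in Table RHCF.6.7 against the appendices as printed**

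| Item in the table | Appendix cited | What that appendix holds | Where the list is | Cited minus actual |
|---|---|---|---|---|
| Anti-infective medications | 8 | Opportunistic-infection terms | 7 | 1 |
| Opportunistic infections | 9 | Anaphylaxis Criterion 2 terms | 8 | 1 |
| Criterion 2 terms | 10 | Hypersensitivity terms and exclusions | 9 | 1 |
| Hypersensitivity exclusions | 11 | IBD terms | 10 | 1 |
| IBD non-specific terms | 11 | IBD terms | 11 | 0 |

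The SAP revision history records that Version 2 removed Appendix 2, which moves every later appendix up by one and explains the pattern. The IBD reference is already right, so one table uses Appendix 11 for two different lists, and a uniform shift of every pointer would break the correct one.

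**2. What the wrong exclusion pointer does**

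- Injection-site terms on the Appendix 10 exclusion list: 7 (dermatitis, eczema, hypersensitivity, rash, recall reaction, urticaria, vasculitis).
- Terms in Appendix 11: 36. Overlap with those 7: 0.
- Injection-site terms removed by the list: 7 with the pointer corrected, 0 as printed.

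The table's rule takes narrow terms only, and the SAP does not show which of the 7 are narrow. The number admitted by a literal reading is therefore somewhere from 0 to 7 and cannot be fixed from the documents.

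**3. The two scopes side by side**

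| | Table RHCF.6.7 | Appendix 10 |
|---|---|---|
| Hypersensitivity SMQ | Narrow terms, less exclusions | Broad and narrow terms, less exclusions |
| Anaphylaxis | Criterion 1 or Criterion 2 | Broad and narrow terms of the Anaphylactic reaction SMQ |
| Angioedema SMQ | Not named | Broad and narrow terms |
| Severe cutaneous adverse reactions SMQ | Not named | Broad and narrow terms |

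Correcting the pointer leaves this difference in place.

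**4. A related inconsistency in Appendix 9**

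Category A of the Criterion 2 terms includes 5 injection-site terms (dermatitis, hypersensitivity, rash, urticaria, vasculitis). All 5 are among the 7 that Appendix 10 excludes. Category B includes cough. An injection-site rash and a cough, nearly coincident and within 1 day of an injection, would meet the A-plus-B combination as a potential anaphylaxis case. That fits poorly with the restriction to events not localized to the injection site, and correcting the pointers does not change it.

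**The case against.** The strongest reply is that this is a renumbering slip which nobody would follow literally. The SAP's own list of appendices gives the right numbers, the Appendix 10 list is plainly headed as exclusions from the Hypersensitivity SMQ, and the table itself says the events are not localized to the injection site. That largely stands. A reader might infer that injection-site events would be counted as systemic hypersensitivity. The documents do not support this, because it requires applying the bowel list as printed and ignoring that restriction, and the number of narrow injection-site terms is unknown. Nor would opportunistic infections realistically be defined by the anaphylaxis list: the table describes terms from the infections and investigations organ classes, and only Appendix 8 fits.

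A second reply is that the two scopes may not conflict. SAP 6.15.3.1 says summaries will show both a broad classification, which pools broad and narrow terms, and a narrow one. Appendix 10 could be the broad search and the table the narrow tabulation. This is possible, but the SAP does not say so, and the Appendix 10 wording is that of a definition. It also means a reader should not infer that the narrow definition is the right one.

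A third reply is that the PSAP supersedes the SAP. That clause covers later changes to term lists or analyses; this inconsistency is in the current text. The revision history says both Table RHCF.6.7 and these appendices were aligned to PSAP Version 8, so it does not settle which scope the PSAP supports.

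Finally, SAP 6.15 calls safety p-values descriptive, and injection-site reactions have their own tables. Both points are right and limit the stakes.

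**Conclusion.** Two defects are established on the face of the SAP. Four pointers in Table RHCF.6.7 are one too high, and one of them attaches the IBD list to the operative rule for a special-interest event. Hypersensitivity also has two stated scopes, with nothing saying which governs the between-arm tabulation.

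The size is 7 injection-site exclusions lost on a literal reading, with 0 to 7 of them relevant under the narrow-term rule. The difference between the two scopes cannot be counted without the SMQ contents. The counts of 7, 36 and 5 rest on the appendix lists as they appear in the available text.

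The effect is confined to descriptive safety tabulations and safety subgroup tests. The primary and major secondary analyses are untouched. The text should be corrected because the rule as written is wrong, but nothing here shows that a reported count would in fact be wrong.

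**What to change.** - In Table RHCF.6.7, change the four pointers: anti-infectives to Appendix 7, opportunistic infections to Appendix 8, Criterion 2 terms to Appendix 9, and hypersensitivity exclusions to Appendix 10. Leave the IBD pointer at Appendix 11.
- State which hypersensitivity definition governs the between-arm tabulation and the subgroup tests, and label the other (for example, as the broad search described in SAP 6.15.3.1). The sponsor should confirm the choice against the PSAP, which is not part of the documents.
- Reconcile the 5 injection-site terms in Appendix 9 Category A with the statement that these events are not localized to the injection site: either remove them or explain why they are kept for screening.

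The cost is SAP text and the matching programming specification. No new data or design change is needed, and no efficacy analysis changes.

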7.3. Blinding

This is an open-label study where treatment allocation is revealed after randomization. Specifically:

- A blinded assessor will complete the following assessments:
 - o TJC/SJC
 - o Psoriasis Area and Severity Index (PASI)
 - Percentage of BSA
 - o Enthesitis
 - o LDI-B
 - NAPSI Fingernails
 - o sPGA

The blinded rater must not know the patient's treatment allocation and is not allowed to be otherwise involved in the study procedures.

The patients will be clearly instructed not to communicate with the blinded assessor except for communication required to conduct the blinded data assessment. During each procedure conducted by a blinded assessor, a third person from the study site (eg, a nurse) will be present to observe and document that blinding of the assessor is maintained. If a blinded assessor is unintentionally unblinded, he/she must be replaced as an assessor.

The availability of a blinded assessor is a prerequisite for study site selection.

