Cerebro-cardiovascular Events	
Cerebro-cardiovascular events will be externally adjudicated by the CEC at the Cleveland Clinic, as outlined in the Manual of Operations. The CEC will adjudicate investigator-reported events selected for adjudication and render an assessment as to whether the event represents a confirmed event (meeting the event definition with all necessary documentation), a non-event (does not meet the event definition and likely represents an alternative or nonevent diagnosis), or lacks sufficient documentation for confirmation of an event. All events which qualify for CEC adjudication will be used for the analysis of cerebro-cardiovascular events. The categories and subcategories of adjudicated events used for the analysis will include the following:
 
 • Cardiovascular 
 ○ Death (Cardiovascular) ○ MI ○ Hospitalization for Unstable Angina ○ Hospitalization for Heart Failure ○ Serious Arrhythmia ○ Hospitalization for Hypertension ○ Resuscitated Sudden Death ○ Cardiogenic Shock due to Myocardial Infarction ○ Coronary Revascularization • Neurologic 
 ○ Cerebrovascular Event: Transient Ischemic Attack or Stroke (Hemorrhagic, Ischemic, and Undetermined) • Peripheral Vascular Events 
 ○ Peripheral Arterial Event ○ Peripheral Revascularization 
Events will be analyzed using MedDRA PT nested within the CEC assessment (confirmed event, no event, or insufficient documentation for event determination) and the subcategory. Subcategories of stroke (Hemorrhagic Stroke, Ischemic Stroke, and Unknown Stroke Type) will be displayed in the analyses nested within stroke. Subcategories of Serious Arrhythmia (Atrial Arrhythmia, Ventricular Arrhythmia, Heart Block, Other, Unknown) will be displayed nested within Serious Arrhythmia.
	
Open-Label Treatment Period (Safety Population): TEAE by PT within Subcategory

MACE	
MACE (requiring adjudication as defined above) is defined as:
 
 • Vascular death (including cardiovascular and cerebro-vascular causes excluding hemorrhagic deaths outside of the central nervous system) • Non-fatal myocardial infarction 	
Open-Label Treatment Period (Safety Population): TEAE by maximum severity PT within Category

Special Safety Topic	Definition/Derivation	Analysis/Summary/Listing

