Depression	
Depression and suicide/self-injury is defined using the PTs from the Depression and suicide/self-injury SMQ as specified in MedDRA (SMQ: 20000035, which includes the sub-SMQs: 20000037
	
Open-Label Treatment Period (Safety Population):

Special Safety Topic	Definition/Derivation	Analysis/Summary/Listing
	[Suicide/self-injury] and 20000167 [Depression (excluding suicide and self-injury)]).	TEAE by PT within SMQ
IBD	IBD will be identified using the following subcategory and MedDRA PTs. The narrow terms are considered IBD. Medical reviews of patients identified with broad terms are needed for final determination of patients with IBD. IBD Specific Terms (Narrow terms) 
 • Inflammatory Bowel Disease: Inflammatory bowel disease • Crohn’s Disease: Crohn’s disease • Ulcerative Colitis: Acute hemorrhagic ulcerative colitis; Colitis ulcerative; Proctitis ulcerative IBD Non-Specific Terms: The PTs in this category are listed in Appendix 11 .	Open-Label Treatment Period (Safety Population): TEAE by PT within subcategory
ILD	ILD is defined using the following terms: 
 • Narrow terms in the Interstitial lung disease SMQ (20000042) • Additional 6 PTs from Eosinophilic pneumonia SMQ (20000157): 
 ○ Angiolymphoid hyperplasia with eosinophilia (Narrow) ○ Eosinophilic bronchitis (Narrow) ○ Hypereosinophilic syndrome (Narrow) ○ Loeffler’s syndrome (Narrow) ○ Pulmonary eosinophilia (Narrow) ○ Pulmonary vasculitis (Narrow) 	Open-Label Treatment Period (Safety Population): TEAE by PT by maximum severity by PT within interstitial lung disease

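### Suspected IBD goes to a blinded external committee under the protocol, but neither the protocol nor the SAP specifies an analysis of the committee's decisions

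*SAP*

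**What the plan says.** **Protocol 9.2.1.1.** IBD is on the list introduced by "Adverse events of special interest for ixekizumab are". Data on suspected cases "will be collected and the events will be adjudicated by an external CEC made up of gastroenterologists with expertise in IBD". The section then states the committee's purpose: "The role of the CEC is to adjudicate defined clinical events, in a blinded, consistent, and unbiased manner throughout the course of a study".

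**Protocol 7.3.** "This is an open-label study where treatment allocation is revealed after randomization". The blinded assessors named there carry out efficacy assessments; reporting adverse events is not among their tasks.

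**SAP 6.15.3.1, Table RHCF.6.7, IBD row.** "IBD will be identified using the following subcategory and MedDRA PTs". The rule for deciding cases is: "The narrow terms are considered IBD. Medical reviews of patients identified with broad terms are needed for final determination of patients with IBD". The planned output is a count of treatment-emergent events by preferred term within subcategory, and the row's subcategories are groups of preferred terms. The broad terms are in SAP Appendix 11 and include colitis, anal abscess and many kinds of fistula.

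**Same table, cerebro-cardiovascular row.** "All events which qualify for CEC adjudication will be used for the analysis of cerebro-cardiovascular events". Events are nested within the committee's assessment: confirmed, not an event, or too poorly documented to decide.

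**The concern.** The two documents name different deciders for the same event. The protocol gives the classification of suspected IBD to blinded outside experts. The SAP gives it to the site's reported term when that term is narrow, and to an unspecified medical review when it is broad. No output shows the committee's result.

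Investigators know the treatment arm, and they know that IBD is an event of special interest for ixekizumab. Diagnostic labelling could therefore lean one way by arm. Blinded adjudication is the protocol's stated means of making that classification uniform. If the adjudicated outcome is not what gets tabulated, that protection does not reach the comparison with adalimumab. Few IBD cases are likely in a trial of this size, so the classification of one or two patients could decide how the arms compare.

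**Working it through.** The main check is textual: each step from report to table, for the two topics that the protocol sends to adjudication.

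| Step | Cerebro-cardiovascular events | IBD |
|---|---|---|
| Adjudication required (Protocol 9.2.1.1) | Yes, external committee | Yes, external committee of gastroenterologists |
| Blinded (Protocol 9.2.1.1) | Yes | Yes |
| Adjudication mentioned in the topic's row of SAP Table RHCF.6.7 | Yes | No |
| Who decides what counts (same table) | The committee | Narrow term: the term as reported. Broad term: medical review, reviewer and blinding not stated |
| Results split by committee assessment (same table) | Yes | No |
| Adjudication eCRF pages named | Yes, in the MACE row | No |

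The output columns of the two rows have nearly the same form, events by preferred term within subcategory. The difference lies in the definition text. The cerebro-cardiovascular definition nests events in the committee assessment, while the IBD definition builds its subcategories from preferred terms alone. The IBD output therefore cannot be read as containing the committee's result by implication.

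Other places where an adjudicated IBD analysis might have been specified:

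- **Protocol 10.3.4.1** plans to find potential events of special interest from a standardised MedDRA query or a sponsor term list. It mentions no adjudicated IBD outcome.
- **Protocol Appendix 1** describes the committee's job as adjudicating cerebrocardiovascular events only, which does not fit 9.2.1.1.
- **SAP 6.15.3.1** lets a program safety analysis plan (PSAP) override the SAP when the terms or analysis for a special topic change. The PSAP is not among the documents.
- **SAP Section 3** records that the IBD wording was updated in Version 2 to match the most recent PSAP. The updated row still has no adjudicated analysis.

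So the adjudication is specified and an analysis of it is not. The inconsistency starts within the protocol and carries into the SAP.

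**Size of one reclassification.** The plan states no IBD incidence, so there is no figure of its own to reproduce. Inputs: 275 patients per arm (Protocol 10.1) and an assumed incidence of 0.4% to 1%.

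- Expected patients per arm: 0.004 × 275 = 1.1; 0.01 × 275 = 2.75.
- Change in an arm's rate from one reclassified patient: 1/275 = 0.36 percentage points.
- As a share of the expected count: 1/2.75 = 36% at the higher incidence; 1/1.1 = 91% at the lower.

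This shows how sensitive the comparison is to one decision. It does not estimate how often the committee would overturn a reported term; the documents give no basis for that.

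**The case against.** **A reader might infer that the committee's IBD decisions will never be analysed.** The documents do not establish that. The PSAP may supersede the SAP on this topic and was not available. What they support is that neither the protocol nor the SAP specifies such an analysis. The Version 2 alignment makes it less likely that the PSAP of that time held one, but does not rule it out.

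**A reader might infer that the SAP simply departs from the protocol.** This is only partly so. The SAP's use of term lists follows Protocol 10.3.4.1, and 9.2.1.1 requires adjudication without saying that the analysis must be based on it. That stands, and it is why the protocol needs a correction too. It does not remove the gap: finding candidates by term and then adjudicating them are compatible steps, as the cerebro-cardiovascular row shows.

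**A reader might infer that the sponsor carries out the medical review.** The text does not say so. The fair criticism is that reviewer, independence and blinding are all undefined.

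**A reader might infer that adjudication would remove open-label bias.** It acts only on events already suspected and collected. It can correct the label on a reported event, but cannot recover a case that was never suspected or investigated.

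**The consequence is limited.** SAP 6.15 treats safety p-values as descriptive flags unless a hypothesis was prespecified, and none is stated for IBD. By-patient listings of treatment-emergent events, serious events and events leading to discontinuation (SAP 6.15.2.1 and 6.15.3) keep individual reports visible, though no listing of the committee's decisions is specified. This limits the weight of the point without answering it.

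**Conclusion.** The point stands as a gap in specification. The protocol sets up blinded expert adjudication of suspected IBD, but neither document says how the result enters the analysis. As written, classification in the open-label comparison rests on site-reported terms and an undefined review. The gap is particular to IBD, because the other adjudicated topic is analysed by committee assessment.

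It should be corrected, but it bears on one descriptive safety topic; the primary and major secondary efficacy tests are untouched. The sizes above, 0.36 percentage points and about 36% to 91% of an arm's expected count per reclassified patient, depend on the assumed incidence of 0.4% to 1%. The conclusion also assumes that the PSAP contains no adjudicated IBD analysis. If it does, a cross-reference in the SAP would close the main gap and leave only Protocol Appendix 1 to align.

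**What to change.** - In the IBD row of SAP Table RHCF.6.7, tabulate events by treatment group, nested within committee assessment (confirmed, not confirmed, insufficient documentation) and disease type (Crohn's disease, ulcerative colitis, other).
- Keep the preferred-term table as supportive.
- Where an event was adjudicated, let the committee's decision replace the medical review. For any review that remains, state who does it and whether they are blinded to treatment.
- Amend Protocol Appendix 1 so that the committee's remit includes IBD, and add a sentence to Protocol 10.3.4.1 that adjudicated outcomes will be analysed.
- State with the results that adjudication does not correct differences between arms in suspicion or work-up.

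The cost is one revised SAP row, one extra output and two short protocol edits. The protocol already requires the data and the adjudication, so nothing further is asked of patients.
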